11.6.3 Exploratory Endpoints

- The statistical analysis of the exploratory objectives will be descriptive.

12 REGISTRATION GUIDELINES

Study-related screening procedures can only begin once the patient has signed a consent form.

Patients must meet all of the eligibility requirements listed in Section 5 prior to registration.

Patients must be registered before receiving any study treatment and must begin treatment within five working days after registration.

To register an eligible patient at HCI, complete a Clinical Trials Office Patient Registration Form, and submit to [contact]. To register a patient at a site outside of HCI, complete a Clinical Trials Office Patient Registration Form, and submit to [contact].

13 DATA SUBMISSION SCHEDULE

The Case Report Forms (CRFs) are a set of (electronic or paper) forms for each patient that provides a record of the data generated according to the protocol. CRF's should be created prior to the study being initiated and updated (if applicable) when amendments to the protocol are IRB approved. These forms will be completed on an on-going basis during the study. The medical records will be a source of verification of the data. During the study, the CRFs will be monitored for completeness, accuracy, legibility, and attention to detail by a member of the Research Compliance Office. The CRFs will be completed by the Investigator or a member of the study team as listed on the Delegation of Duties Log. The data will be reviewed no less than annually by the Data and Safety Monitoring Committee. The Investigator will allow the Data and Safety Monitoring Committee or Research Compliance Office personnel access to the patient source documents, clinical supplies dispensing and storage area, and study documentation for the above-mentioned purpose. The Investigator further agrees to assist the site visitors in their activities.

Data capture should be restricted to endpoints and relevant patient information required for planned manuscripts.

14 CORRELATIVE STUDIES

To support exploratory objectives and correlative studies, blood and tissue samples will be collected at the time points indicated on the Schedule of Events. After completion of the described correlative studies, any remaining blood or tissue will be stored for future unspecified cancer research. With the participant's approval and as approved by the Institutional Review Board (IRB), de-identified biological samples will be stored at Huntsman Cancer Institute's Biorepository.

At the time of consent, subjects will be given the opportunity to authorize the biobanking of their remaining samples for use in future undisclosed cancer research. During the conduct of the study, an individual participant can choose to withdraw consent to have biological specimens stored for future research. However, the withdrawal of consent with regard to biosample storage may not be possible after the study is completed.

14.1 Bone marrow aspirate samples

Up to 20 mLs of bone marrow aspirate will be collected at the time points noted on the Schedule of Events. These samples will be used to explore the changes in allele burden, mechanisms of resistance, and cellular changes. Testing may include, but is not limited to:

- Whole exome sequencing
- RNA sequencing
- Flow cytometry

- Immunohistochemistry
- Immune cell enumeration and characterization
- Immunoblot

Specimen collection and processing instructions can be found in the lab manual.

14.2 Skin punch biopsy

A skin punch biopsy will be collected at screening for DNA extraction to establish a germline control for whole-exome sequencing.

Testing may include, but is not limited to:

- Whole exome sequencing

Specimen collection and processing instructions can be found in the lab manual.

14.3 Blood correlative studies

Up to 60 mL will be collected for required samples at the time-points noted on the Schedule of Events.

These samples will be used to assess the effect cobimetinib treatment has on molecular and phenotypic disease characteristics. They will also be used to evaluate and characterize mechanisms of therapy resistance and to identify potential biomarkers of response.

Testing may include, but is not limited to:

- Flow cytometry
- Cytokine/chemokine/interferon assays
- Immunohistochemistry
- Immune cell enumeration and characterization
- Colony assays
- Single-cell sequencing to evaluate clonal dynamics
- Next-Gen Sequencing

Specimen collection and processing instructions can be found in the lab manual.

15 ETHICAL AND REGULATORY CONSIDERATIONS

15.1 Human Subject Protections

The study will be conducted in accordance with the appropriate FDA, IRB, ICH GCP, and other federal and local regulatory requirements, as applicable. Informed consent will be obtained from all research participants before performing any study procedures using the most recent IRB-approved version. All patients must be at least 18 years of age to participate.

15.2 Institutional Review

Before study initiation, the investigator must have written and dated approval/favorable opinion from the IRB/IEC for the protocol, consent form, subject recruitment materials (eg, advertisements), and any other applicable patient-facing documents. The investigator should also provide the IRB/IEC with a copy of the Investigator Brochure or product labeling information.

The investigator or designee should provide the IRB/IEC with reports, updates, and other information (eg, expedited safety reports, amendments, and administrative letters) according to regulatory requirements or institution procedures.

15.3 Data and Safety Monitoring Plan

A Data and Safety Monitoring Committee (DSMC) is established at Huntsman Cancer Institute (HCI) to ensure the well-being of patients enrolled on Investigator Initiated Trials that do not have an outside monitoring review. The roles and responsibilities of the DSMC are outlined in the NCI-approved Data and Safety Monitoring (DSM) plan. The activities of the committee include reviewing adverse events (including SAEs), deviations, important medical events, significant revisions or amendments to the protocol, and approving cohort/dose escalations. If the DSMC and/or the PI have concerns about unexpected safety issues, the study will be stopped and will not be resumed until the issues are resolved. The DSMC also reviews and approves audit reports generated by the Research Compliance Office.

This study is classified as high risk per the NCI-approved DSM plan.

Each high-risk study will be assigned a physician member of the DSMC as a medical monitor, or in rare cases, an external medical monitor. The medical monitor will be notified of all serious adverse events (SAEs). Specific notifications will also be issued when dose-limiting toxicity is encountered and when the MTD dose is defined. Approval of the medical monitor is required for all dose escalations. All serious adverse events (SAEs) occurring in patients treated at HCI or its affiliates will also be reviewed by the full DSMC monthly. The full committee will also review all toxicities for patients on treatment.

Each high-risk study will also be assigned a dedicated research compliance officer who will monitor the trial. High-risk studies will be monitored by RCO personnel after the first patient is enrolled and every three months thereafter during active enrollment. The RCO monitor will review the study status and summarize enrollment, toxicities, SAEs, dose-escalation, statistical endpoints (e.g., stopping rules), deviations, etc. for the full DSMC membership at the regularly scheduled meetings. Amendments that increase risk, change dosing, or impact study objectives will be reviewed by the DSMC and approved by the PRMC and IRB. High-risk trials will be formally reviewed by the DSMC after the first patient is enrolled and then quarterly thereafter.

An initial audit of high-risk studies will be conducted by the RCO approximately one year after enrollment begins and annually thereafter. Audits of high-risk studies may be conducted more frequently as requested by the DSMC, IRB, PRMC, RCO management, or the PI.

15.4 Adverse Events (AEs)

An AE is any unfavorable and unintended sign (including an abnormal laboratory finding), symptom, or disease temporally associated with the use of an investigational medicinal product (IMP) or other protocol-imposed intervention, regardless of attribution.

This includes the following:

- AEs not previously observed in the subject that emerged during the protocol-specified AE reporting period, including signs or symptoms associated with CMML that were not present prior to the AE reporting period.
- Complications that occur as a result of protocol-mandated interventions (e.g., invasive procedures such as bone marrow biopsies).
- Preexisting medical conditions (other than the condition being studied) judged by the investigator to have worsened in severity or frequency or changed in character during the protocol-specified AE reporting period.

Collection of adverse events will begin with the first dose of study medication and end 30 after the last dose of study drug (or until new cancer treatment is initiated).

Information about all adverse events, whether volunteered by the subject, discovered by investigator questioning, or detected through physical examination, laboratory test, or other means, will be collected, recorded, and followed as appropriate.

The adverse event should be evaluated to determine:

1. The severity grade based on CTCAE v5.0 (grade 1-5)
2. Its relationship to the study drug (definite, probable, possible, unlikely, not related)
3. Its duration (start and end dates or if continuing at the final exam)
4. Action taken (no action taken; study drug dosage adjusted/temporarily interrupted; study drug permanently discontinued due to this adverse event; concomitant medication taken; non-drug therapy given; hospitalization/prolonged hospitalization)
5. Whether it constitutes an SAE

All adverse events will be treated appropriately. Such treatment may include changes in study drug treatment as listed in the dose modification section of this protocol (see section 7.2 for guidance). Once an adverse event is detected, it should be followed until its resolution, and assessment should be made at each visit (or more frequently, if necessary) of any changes in severity, the suspected relationship to the study drug, the interventions required to treat it, and the outcome.

Information about common side effects already known about cobimetinib is described in the Drug Information (section 3), the investigator brochure, and the current product insert. This information will be included in the patient informed consent and will be discussed with the patient during the study as needed.

All adverse events will be immediately recorded in the patient research chart.

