2 BACKGROUND

2.1 Chronic Myelomonocytic Leukemia

Chronic myelomonocytic leukemia (CMML), with an estimated incidence of 4 cases per 100,000 persons per year, accounts for the vast majority of hematologic malignancies classified as myelodysplastic/myeloproliferative (MDS/MPN) neoplasms.^{1,2} As a disease group, MDS/MPN is characterized by features consistent with ineffective hematopoiesis, such as cytopenias, but also exhibit signs characteristic of myeloid hyperplasia, such as splenomegaly, leukocytosis and debilitating constitutional symptoms. CMML is poor-risk

Table 1: WHO 2022 diagnostic criteria for CMML.

Prerequisite criteria
1. Persistent absolute ($\geq 0.5 \times 10^9/L$) and relative ($\geq 10\%$) peripheral blood monocyto-sis.
2. Blasts constitute $< 20\%$ of the cells in the peripheral blood and bone marrow.
3. Not meeting diagnostic criteria of chronic myeloid leukaemia or other myeloproliferative neoplasms.
4. Not meeting diagnostic criteria of myeloid/lymphoid neoplasms with tyrosine kinase fusions.
Supporting criteria
1. Dysplasia involving ≥ 1 myeloid lineages.
2. Acquired clonal cytogenetic or molecular abnormality.
3. Abnormal partitioning of peripheral blood monocyte subsets.
Requirements for diagnosis
- Pre-requisite criteria must be present in all cases.
- If monocyto-sis is $\geq 1 \times 10^9/L$: one or more supporting criteria must be met.
- If monocyto-sis is ≥ 0.5 and $< 1 \times 10^9/L$: supporting criteria 1 and 2 must be met.
Subtyping criteria
- Myelodysplastic CMML (MD-CMML): $WBC < 13 \times 10^9/L$
- Myeloproliferative CMML (MP-CMML): $WBC \geq 13 \times 10^9/L$
Subgrouping criteria (based on percentage of blasts and promonocytes)
CMML-1: $< 5\%$ in peripheral blood and $< 10\%$ in bone marrow
CMML-2: $5\text{--}19\%$ in peripheral blood and $10\text{--}19\%$ in bone marrow

leukemia of older adults, with an average age of diagnosis of 72 years.³ Even with currently available therapies, the median overall survival is dismal, ranging from 12-29 months.¹ The inferior survival outcomes in CMML are primarily driven by a high risk of progression to acute myeloid leukemia (AML). Allogeneic stem cell transplant for CMML is potentially curative, but relapse rates and transplant-related mortality are high, and few patients are eligible due to advanced age and co-morbidities.

Diagnostic criteria for CMML according

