7.2 Dose Modifications and Guidelines for Adverse Event Management

Patients experiencing adverse events attributed to study drug may undergo dose modifications for toxicity management. **Dose modification guidelines are provided below for adverse events considered to be related (definitely, probably, or possibly related) to the study medication.** When considering hematologic adverse events, baseline (C1D1) values should be taken into consideration where noted below before initiating dose modifications.

Table 4: Guidelines for Adverse Event Management

Toxicity and Severity	Supportive care and dose adjustment guidelines
Thrombocytopenia	
Grade 1 or 2	Maintain dose. Rule out other causes including drug effects.
Grade 3 without bleeding	Maintain dose. Rule out other causes including drug effects.
Grade 4 without bleeding and baseline platelet count $\geq 25,000/\mu\text{L}$	
Rule out other causes including drug effects. Platelet transfusion is allowed if clinically indicated.
 
For the first occurrence: hold cobimetinib until \leq Grade 3 or baseline and reduce by 1 dose level.
 
If recurrent, the investigator may decide to continue cobimetinib dosing without dose reductions and/or interruptions \, provided that platelet counts and bleeding symptoms/signs are closely monitored. Additional dose holds/reductions for thrombocytopenia are allowed if felt to be significantly impacting patient quality of life (e.g. patient is transfusion-dependent).

Grade 4 without bleeding and baseline platelet count $< 25,000/\mu\text{L}$	
Rule out other causes.. If persistent, the investigator may decide to continue cobimetinib dosing without dose reductions and/or interruptions, provided that platelet counts and bleeding symptoms/signs are closely monitored. Platelet transfusion is allowed if clinically indicated... Dose holds/reductions for severe thrombocytopenia are allowed if felt to be significantly impacting patient quality of life (e.g. patient is transfusion-dependent).

Grade ≥ 3 with bleeding	
Interrupt cobimetinib dosing and check platelet counts weekly until the bleeding has stopped, the patient is clinically stable, and the platelets have recovered to Grade ≤ 3 or baseline. Platelet transfusion is allowed if clinically indicated. When resuming cobimetinib, reduce by 1 dose level.

Neutropenia	

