15.4.1 Instructions for Recording Adverse Events

Investigators should use correct medical terminology/concepts when reporting AEs or SAEs. Avoid colloquialisms and abbreviations.

Eliciting Adverse Events

A consistent methodology for eliciting AEs at all subject evaluation time points should be adopted. Examples of non-directive questions include:

- “How have you felt since your last clinical visit?”
- “Have you had any new or changed health problems since you were last here?”

Diagnosis vs. Signs and Symptoms

If known at the time of reporting, a diagnosis should be reported rather than individual signs and symptoms (e.g., record only liver failure or hepatitis rather than jaundice, asterixis, and elevated transaminases). However, if a constellation of signs and/or symptoms cannot be medically characterized as a single diagnosis or syndrome at the time of reporting, it is acceptable to report the information that is currently available. If a diagnosis is subsequently established, it should be reported as follow-up information.

Preexisting Medical Conditions

A preexisting medical condition is one that is present at the start of the study. Such conditions should be reported as medical and surgical history. A preexisting medical condition should be re-assessed throughout the trial and reported as an AE or SAE only if the frequency, severity, or character of the condition worsens during the study. When reporting such events, it is important to convey the concept that the preexisting condition has changed by including applicable descriptors (e.g., “more frequent headaches”).

Abnormal Test Findings

Abnormal test finding, such as incidental image findings, should only be listed as an adverse event if it meets the following criteria:

- Is associated with accompanying symptoms; and/or
- Requires additional testing or intervention; and/or
- Leads to changes in study therapy dosing; and/or
- Leads to the addition or change of a concomitant medication or therapy; and/or
- Is considered an adverse event by the treating investigator.

An abnormal test considered to be an error should not be listed as an adverse event. Repeating a test due to an abnormal result in the absence of any of the criteria above does not require listing as an adverse event.

Hospitalizations for Medical or Surgical Procedures

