Any AE that results in hospitalization or prolonged hospitalization should be documented and reported as an SAE. If a subject is hospitalized to undergo a medical or surgical procedure as a result of an AE, the event responsible for the procedure, not the procedure itself, should be reported as the SAE. For example, if a subject is hospitalized to undergo coronary bypass surgery, record the heart condition that necessitated the bypass as the SAE.

For hospitalizations that do not require reporting see section 15.5

Deaths

All deaths that occur during the protocol-specified AE reporting period (15.4.1), regardless of attribution, will be reported to the appropriate parties. When recording a death, the event or condition that caused or contributed to the fatal outcome should be reported as the single medical concept. All deaths that occur during the protocol-specified AE reporting period must be reported as follows:

- Death should be reported as an SAE within one working day of first knowledge and documented in the patient's research chart and eCRF, regardless of cause.
- The cause of death should be reported as an SAE, whether it was the result of an AE, was due to disease progression, or the cause is unknown.
- If an autopsy is performed, a copy of the results should be included in the patient's research chart to confirm the cause of death.

Deaths occurring after the protocol defined safety follow up period after the administration of the last dose of study drug should be documented in the eCRF. If the death occurred as a result of an event that started after the defined safety follow up period and the event is considered to be due to late-onset toxicity to study drug, then it should also be reported as an SAE. (See Section 15.4.1 AE Reporting Period)

Assessment of Severity of Adverse Events

The adverse event severity grading scale for the NCI CTCAE (v5.0) will be used for assessing adverse event severity. The below table should be used for assessing severity for adverse events that are not specifically listed in the NCI CTCAE.

Table 8: Adverse event grading scale for events not specifically listed in the NCI CTCAE

Grade	Severity
1	Mild; asymptomatic or mild symptoms; clinical or diagnostic observations only; or intervention not indicated
2	Moderate; minimal, local, or non-invasive intervention indicated; or limiting age-appropriate instrumental activities of daily living ^a

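### Section 15.4 does not settle whether worsening of a CMML sign already present at baseline is an adverse event, so non-serious worsening that prompts no action may go unrecorded

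*Combined protocol and SAP*

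**What the plan says.** The opening sentence of Section 15.4 is wide: "An AE is any unfavorable and unintended sign (including an abnormal laboratory finding), symptom, or disease temporally associated with the use" of the product or a protocol-imposed intervention, whatever the attribution. A bullet list follows, introduced by "This includes the following". Two bullets bear on CMML:

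- Bullet 1 covers events that emerge in the reporting period, "including signs or symptoms associated with CMML that were not present prior to the AE reporting period".
- Bullet 3 covers "Preexisting medical conditions (other than the condition being studied) judged by the investigator to have worsened in severity or frequency".

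Section 15.4.1 gives the recording rules. A preexisting condition is "reported as an AE or SAE only if the frequency, severity, or character of the condition worsens during the study", with no exception for CMML. An abnormal test is listed only if it comes with symptoms, needs further testing or intervention, changes study dosing or other therapy, or is considered an AE by the investigator.

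Section 7.2 treats low counts as adverse events to be read against baseline: "When considering hematologic adverse events, baseline (C1D1) values should be taken into consideration where noted below before initiating dose modifications". Section 2.1 describes the disease group by "ineffective hematopoiesis, such as cytopenias, but also exhibit signs characteristic of myeloid hyperplasia, such as splenomegaly, leukocytosis and debilitating constitutional symptoms". AE frequency by seriousness, severity, duration and relationship is a secondary endpoint (Section 1.2.1), analyzed descriptively (Section 11.6.2).

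**The concern.** Cytopenias and constitutional symptoms belong to CMML, and many patients can be expected to have some of them at C1D1. For these signs, drug toxicity and disease are hard to tell apart. The general definition lets the event be recorded first and its cause judged afterwards in the relationship field. The exception in bullet 3 can be read as asking for the cause first: if the investigator thinks the worsening is CMML, nothing is recorded.

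The trial has one arm per cohort and may run at up to three centers. With no control group, under-recording cannot be seen by comparison, and two sites could follow different sentences of the same protocol. At stake is whether the AE tables describe what happened to patients or partly reflect how each site read Section 15.4.

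**Working it through.** No sample size, power or error rate enters this point, so the check sets the provisions side by side.

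**Step 1. Trace three kinds of event.**

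| Event | Opening sentence, 15.4 | Bullets, 15.4 | Preexisting conditions, 15.4.1 |
|---|---|---|---|
| New CMML sign | AE | AE (bullet 1) | Not applicable |
| Preexisting non-CMML condition worsens | AE | AE (bullet 3) | AE |
| Baseline CMML sign worsens | AE | Not named in bullet 1; excepted in bullet 3 | AE |

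Only the third row conflicts.

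**Step 2. Remove from that row what other provisions catch.**

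- Serious worsening is reported whether or not it is related (Section 15.5).
- Test results that change dosing, need intervention or change other therapy are listed (Section 15.4.1). A transfused anemia is an example. So is a drug-related first Grade 4 thrombocytopenia from a baseline of at least 25,000/µL, for which Table 4 prescribes a hold and reduction.
- Symptoms that lead to dose modification are handled as adverse events (Sections 7.2 and 10.3).
- Grade 3 or higher rash and diarrhea, among others, are events of special interest with no baseline-disease exception (Section 15.4.2).

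**Step 3. See what remains.** Non-serious worsening that prompts no action remains. Table 4 makes this plausible for blood counts. It keeps the dose for Grade 3 thrombocytopenia without bleeding and for afebrile Grade 4 neutropenia with a baseline count below 500. It also allows unchanged dosing for Grade 4 thrombocytopenia without bleeding when baseline platelets are below 25,000/µL. In those rows the dosing trigger need not fire. Unless work-up or treatment is needed, listing rests on whether the investigator considers the result an AE, which leads back to the ambiguous definition. The rule that Grade 4 and 5 events are serious does not clearly close the gap: it is a footnote to Table 8, which grades events that CTCAE does not list.

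**Step 4. Check whether the efficacy side picks it up.** Footnote h of Appendix 3 keeps therapy-related cytopenias out of the assessment of progression. A drug-caused fall from a low baseline is therefore not progression, and under one reading of bullet 3 it is not recorded as an AE either.

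**Step 5. Scale.** The documents give neither the share of patients with baseline cytopenia nor the share who worsen, so no count can be derived. At the planned accrual (Section 4.2), one patient whose only event in a table row goes unrecorded lowers that row by:

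- 1/29 = 3.4 percentage points for all patients;
- 1/14 = 7.1 points in the newly diagnosed cohort;
- 1/15 = 6.7 points in the HMA-refractory cohort.

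These are units of effect, not an estimate of how many patients are affected.

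**The case against.** The strongest reply is that the bullets only illustrate. The opening sentence already covers any sign, symptom or laboratory abnormality, and failing to fit a bullet is not exclusion. Bullet 3 also excepts the condition, not each symptom or laboratory value. This is a fair reading, and it rules out the stronger inference that CMML signs count only when new. It does not remove the conflict. If the opening sentence governs alone, the exception in bullet 3 does nothing; a site that gives those words effect is also reading reasonably.

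The second reply is that actionable and serious worsening is captured elsewhere, and that the full safety committee reviews all toxicities for patients on treatment (Section 15.3). The first part stands and narrows the point to Step 3. Committee review depends on what has been recorded.

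A reader might also infer that the toxicity stopping rule is weakened. The documents do not support that. Section 11.3 counts only Grade 3 or higher non-hematologic events that are attributed to therapy, do not improve with standard interventions, and are judged a continuing risk by both the principal investigator and the medical monitor. Cytopenias are outside it. An event the investigator ascribes to CMML would normally fail the attribution test even with the exception deleted. Any lower crossing probability would need an assumed leakage share that the documents do not supply.

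Nor does the death rule add much. "The cause of death should be reported as an SAE, whether it was the result of an AE, was due to disease progression" is a specific provision for fatal outcomes and fits a non-exhaustive list.

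Last, Amendment 6 takes remaining patients off study cobimetinib, and AE collection ends 30 days after the last dose. New wording will therefore have little prospective effect. That is true, and it is the main reason for adding a table built from counts already scheduled.

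**Conclusion.** Section 15.4 is inconsistent with its own opening definition and with Section 15.4.1 on worsening of CMML signs present at baseline. The consequence is limited: non-serious worsening that prompts no action may be recorded at one site and not at another, and where it is left out the secondary AE frequencies are lowered. The endpoint is descriptive; no hypothesis test, sample size or stopping boundary depends on it.

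The direction, where there is an effect, is toward fewer recorded events. The size cannot be stated from the documents, and a claim that the reported rate is biased low by a given number of patients would go beyond them. The conclusion assumes only that some patients enter with cytopenias or symptoms that can worsen, which Section 2.1 supports, and that some sites may give the exception its ordinary meaning.

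**What to change.** 1. In Section 15.4, delete the parenthetical exception in bullet 3 and the matching limit to new signs in bullet 1. State that worsening from baseline of a CMML-associated sign or symptom is recorded as an AE with its attribution.
2. Leave the abnormal-test criteria of Section 15.4.1 in force for laboratory values, and say so, so that the two sections agree. State that progression meeting Appendix 3 remains the efficacy outcome.
3. In Section 11.6.2, add a table of worst on-treatment CTCAE grade and shift from the C1D1 grade for platelets, neutrophils and hemoglobin, overall and by cohort.

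The third item does most of the work for blood counts. It does not depend on the disease-versus-drug judgment, uses the counts scheduled in Table 5 and remains possible after Amendment 6. It needs no re-abstraction, assuming the scheduled counts are in the study database. It has one limit: a patient already at Grade 4 at C1D1 cannot shift upward.

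The cost is a short edit to Section 15.4, one extra table, and somewhat more AE entries, some caused by disease, which the relationship field separates. Sample size and decision rules do not change.
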